### 7.16 Follow-up Day 56 (End-of-Study) or Early Termination Visit

On Day 56 ( $\pm 5$  days), subjects are to return to the clinic and the following procedures are to be performed:

- Complete physical exam ([Section 6.3](#))
- Vital sign measurements (after 5 minutes of rest; sitting blood pressure, heart rate, respiratory rate, oral temperature); abnormal results to be repeated after 5 minutes of rest ([Section 6.5](#))
- Clinical safety laboratory tests (hematology, serum chemistry panel, urinalysis) ([Section 6.7](#))
- Pregnancy test ([Section 6.7](#))
- 12-Lead ECG (to be obtained in triplicate after 5 minutes of rest in the sitting position) ([Section 6.5](#))
- Serum tetanus antibody and VZV antibody; Testing at Day 56 will not be done for any subject whose baseline titer is below the level of detection. See [Section 6.7.3](#) for additional information.
- Immunogenicity sample collection ([Section 6.7](#))
- PDAI Score ([Section 6.4](#))
- PD sample collection ([Section 6.7](#))
  - IgG, IgG subtypes (IgG1-4), IgA, IgM
  - CIC
  - Anti-Dsg (1 and 3) antibody titer
  - C3

- AECA
- RNAseq
- Urine IgG
- Optional skin biopsy ([Section 6.12](#))
- Photography ([Section 6.11](#))
- Concomitant medication assessment ([Section 6.9](#))
- AE assessment ([Section 6.10](#))

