- b: **Vital sign** measurements (sitting blood pressure, heart rate, respiratory rate, and oral temperature) to be obtained after 5 minutes of seated rest. Any abnormal measurements are to be repeated after 5 minutes of rest. On Days 0, 7, 14, 21, and 28 vital sign measurements will be collected immediately prior to the infusion; 15, 30, and 45 minutes after the start of the infusion; at completion of the infusion; and 30 minutes, 1 hour and 2 hours following completion of the infusion.
- c: **Pulse oximetry**: On Days 0, 7, 14, 21, and 28, pulse oximetry to be measured immediately prior to the infusion; 15, 30, and 45 minutes after the start of the infusion; at completion of the infusion; and 30 minutes, 1 hour and 2 hours following completion of the infusion.
- d: **Clinical safety labs**: hematology, clinical chemistry, and urinalysis (see [Section 6.7](#) for a complete list). Full clinical safety lab draws will be collected at Screening and on Days 0, 7, 14, 21, 28, 33, 42 and 56.
- e: **Pregnancy test**: To be performed at time of screening and prior to first dose of SYNT001 on Day 0 and on Day 56 (urine or serum test is acceptable, however, positive urine tests must be confirmed with serum testing.)
- f: Digital 12-lead **ECG** to be obtained after 5 minutes of rest in the supine position and in triplicate at least 1-2 minutes apart (see [Section 6.6](#) for additional information). On Days 0 and 28 to be obtained 5 minutes after the completion of infusion. Day 12 ECG will be collected only if the visit is conducted at the study site.
- g: **Serology**: Testing at Day 56 will not be done for any subject whose baseline titer is below the level of detection. If the Day 56 results are greater than 30% below the baseline value, or if the subject falls below the level of detection, the subject will be re-tested at 1 month after the Follow-Up visit (approximately 2 months after the subject's last dose); if still below the baseline value (or level of detection), the subject will be re-tested after another month (3 months after last dose). Any subject whose baseline value for tetanus or VZV was above the detectable level at baseline, and is not within 30% of the baseline value or is below the detectable level on Day 56 and upon 2 retests (2 and 3 months following last dose of SYNT001), will be referred to their primary care physician for further management. See [Section 6.7.3](#) for additional information.

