#### **6.6 12-Lead Electrocardiogram (ECG)**

Digital 12-lead ECG measurements will be obtained at screening, on Days 0 and 28 at 5 minutes after the completion of the infusion and at the Day 56 (Follow-Up) Visit. Subjects who conduct their Day 12 visit at the investigative site, as opposed to an at-home nurse visit, will have an additional ECG performed. ECGs are to be performed with the subject in a supine position having rested in this position for at least 5 minutes before each reading. ECGs are to be performed in triplicate, each 1 to 2 minutes apart. See [Table 2](#) for timing window allowances with respect to performing ECG.

The following ECG parameters will be collected: PR interval, RR interval, QRS interval, and QT interval. The ECG findings will be evaluated by a qualified physician for the presence of abnormalities (qualitative assessment). The physician will assess each ECG as normal, abnormal/not clinically significant, or abnormal/clinically significant.

Normal QTcF is  $\leq 450$  msec.

Abnormalities in the ECG that appear following therapy or that result in clinical signs and symptoms are considered clinically significant for the purposes of this study and will be recorded on the AE eCRF.

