## 7 STUDY ASSESSMENTS

### 7.1 Screening Period: Day -14 to Day -1

Informed consent must be obtained before any study-specific samples are taken or study-specific tests or evaluations are conducted. The following assessments at the screening visit are to occur within 14 days before dosing. Study eligibility will be based on satisfying all the study inclusion and exclusion criteria.

At the screening visit, information will be collected and subjects will have clinical evaluations as follows:

- Informed consent ([Section 6.1](#))
- Medical history and demographic data ([Section 6.2](#))
- Review inclusion and exclusion criteria ([Section 5.2](#), [Section 5.3](#))
- Complete PE, including height and weight ([Section 6.3](#))
- Vital sign measurements (after 5 minutes of rest; sitting blood pressure, heart rate, respiratory rate, oral temperature); abnormal results to be repeated after 5 minutes of rest ([Section 6.5](#))
- 12-Lead ECG (to be obtained in triplicate after 5 minutes of rest in the supine position) ([Section 6.6](#))
- Clinical safety laboratory tests (hematology, serum chemistry panel, urinalysis) ([Section 6.7](#))
- Pregnancy test ([Section 6.7](#))
- Hepatitis and HIV screen ([Section 6.7](#))
- PD sample collection ([Section 6.7](#))
  - IgG, IgG subtypes (IgG1-4), IgA, IgM
  - Anti-Dsg (1 and 3) antibody titer
- Concomitant medication assessment ([Section 6.9](#))
- AE assessment ([Section 6.10](#))

### 7.2 Enrollment and First Treatment: Day 0

Study Day 0 is defined as the date the subject is administered their first dose of study drug. On Day 0, subjects will be asked to come to the clinic and the following procedures will be performed prior to the first dose of study drug:

- Complete physical exam ([Section 6.3](#))
- Vital sign measurements (sitting blood pressure, heart rate, respiratory rate, oral temperature); to be measured immediately prior to the infusion ([Section 6.5](#))
- Pulse oximetry (to be measured immediately prior to the infusion) ([Section 6.5](#))

- Clinical safety laboratory tests (hematology, serum chemistry panel, urinalysis) ([Section 6.7](#))
- Pregnancy test ([Section 6.7](#))
- Serum tetanus antibody and VZV antibody ([Section 6.7](#))
- PDAI Score ([Section 6.4](#))
- PK baseline sample collection (collected just prior to the start of the study drug infusion) ([Section 6.7](#))
- Immunogenicity sample collection (collected just prior to the start of study drug infusion) ([Section 6.7](#))

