## **12.5 Safety Data**

Safety observations and measurements include AEs, safety laboratory tests, vital sign measurements, PEs, and ECGs.

Treatment-emergent AEs will be summarized using the Medical Dictionary for Regulatory Activities (MedDRA®; Version 19 or higher) System Organ Class (SOC) and preferred term, classified from verbatim terms. The incidence and percentage of subjects with at least 1 occurrence of a preferred term will be included, using the most severe grade. The number of events per preferred term will also be summarized. Causality (relationship to study treatment) will be summarized separately.

AEs, SAEs, and AEs leading to withdrawal, dose modification, or treatment discontinuation will be listed by subject, cohort, and overall per SOC and preferred terms. Duration of AEs will be determined and included in listings, along with action taken and outcome.

Laboratory results will be summarized by cohort. Incidence of laboratory abnormalities will be summarized. The worst on-study grade after the first dose of study drug will be summarized. Results for variables that are not coded will be presented in the listings as below, within, and above the normal limits of the local laboratory.

Vital sign measurements and change from baseline will be summarized at each scheduled time point by cohort using descriptive statistics.

Arithmetic mean of parameters from triplicate ECG will be calculated first for each participant at each planned time point. Then summary statistics of ECG test parameters (mean of triplicate) and change from baseline to each post-dose time point will be calculated. Shift tables for ECG test result category change (normal, abnormal, clinically abnormal) from pre-dose to each post-dose time point showing number and percentage of subjects with movement between categories will be presented by treatment group. Frequency and percentage of subjects experiencing potential QTc prolongation ( $QTcF > 450$ ) will be summarized at each time point by cohort.

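### Section 7.16 has the Day 56/Early Termination ECG taken sitting, while Section 6.6 and Table 1 note f require supine for the same recording

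*Protocol*

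**What the plan says.** Four places in the protocol govern the posture of the Day 56/Early Termination ECG or of the ECG it is compared with.

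- **Section 7.16 (Day 56 or Early Termination visit)** asks for a "12-Lead ECG (to be obtained in triplicate after 5 minutes of rest in the sitting position" and gives Section 6.5, Vital Sign Measurements, as the reference.
- **Section 6.6 (12-Lead ECG)** states the rule for all ECGs: "ECGs are to be performed with the subject in a supine position having rested in this position for at least 5 minutes". The same section schedules them after screening "on Days 0 and 28 at 5 minutes after the completion of the infusion and at the Day 56 (Follow-Up) Visit", so it explicitly covers the Day 56 recording.
- **Table 1, note f**, attached to the whole ECG row including the Day 56/ET column, says the ECG is "to be obtained after 5 minutes of rest in the supine position and in triplicate at least 1-2 minutes apart".
- **Section 7.1 (Screening)** asks for a "12-Lead ECG (to be obtained in triplicate after 5 minutes of rest in the supine position".

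The visit lists for Days 0, 12 and 28 (Sections 7.2, 7.7 and 7.11) do not restate a posture; each refers to Section 6.6.

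In the analysis, Section 12.5 averages each triplicate and says that "change from baseline to each post-dose time point will be calculated". It also tabulates movement between ECG result categories relative to pre-dose, and the number and percentage of subjects with QTcF above 450 at each time point by cohort. Section 4.2 includes ECGs in the primary safety measure.

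**The concern.** A change from baseline describes the subject only if both recordings are made the same way. The protocol fixes posture, rest time and replication for ECGs for that reason. Section 7.16 changes the posture for one visit without saying so or giving a reason, and sends the reader to the wrong procedure section.

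A site working from its visit list would record Day 56 sitting. A site working from the ECG section or the schedule table would record it supine. In the first case the Day 56/ET change mixes any true change with a change of posture. If practice is mixed, part of the variation at that visit becomes a site effect. The ECG parameters listed for collection in Section 6.6 are PR, RR, QRS and QT. Posture is not among them, so sitting and supine recordings may be impossible to separate later without a query.

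Two features make the visit worth protecting. It is the only scheduled recovery ECG, 28 days after the last dose, and it also serves subjects who stop early. In addition, Section 6.6 treats ECG abnormalities appearing after therapy as clinically significant and sends them to the adverse event form, so a posture-related finding could reach the adverse event data as well as the ECG tables.

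**Working it through.** There is no stated figure to reproduce: the protocol makes no sample size calculation and attaches no test to the ECG data. The check sets the instructions for each scheduled ECG side by side.

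| ECG | Visit section | Posture in visit section | Section cited there | Posture in 6.6 and Table 1 note f | Consistent? |
|---|---|---|---|---|---|
| Screening (Day -14 to -1) | 7.1 | supine | 6.6 | supine | yes |
| Day 0, 5 minutes after infusion | 7.2 | not restated | 6.6 | supine | yes |
| Day 12, only if on site | 7.7 | not restated | 6.6 | supine | yes |
| Day 28, 5 minutes after infusion | 7.11 | not restated | 6.6 | supine | yes |
| Day 56 or Early Termination | 7.16 | sitting | 6.5 | supine | **no** |

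**Which comparisons are affected.** The only scheduled pre-dose ECG is the supine triplicate at screening. Against it:

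- Days 0, 12 and 28 match in posture and in triplicate recording.
- Day 56/ET matches if the site follows 6.6 or Table 1, and does not if the site follows 7.16.

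The mismatch can therefore touch 1 of 3 guaranteed post-dose time points (Days 0, 28, 56), or 1 of 4 counting Day 12.

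**Which summaries are affected.** All three Section 12.5 displays at Day 56/ET: mean change, category shift, and the QTcF count. With 8 subjects per cohort, one subject crossing 450 msec moves the cohort percentage by 1/8 = 12.5 percentage points. This shows how coarse the count is; it does not estimate how many subjects would cross.

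**Is it a slip in a single place?** The protocol text is supplied twice. The two copies are not identical (Section 6.7 gives a total blood draw of about 308 mL in one and 311 mL in the other), yet both carry the sitting instruction and the reference to 6.5 in Section 7.16, and both say supine in Section 6.6 and Table 1 note f.

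**The case against.** The strongest reply is that this is a clerical carry-over with little consequence. Vital signs are taken sitting under Section 6.5, and 7.16 cites that section, so the phrase was probably borrowed from the vital-signs text. The ECG section and the schedule table both say supine, and many sites may simply follow them. The ECG analyses are descriptive. The end-of-infusion ECGs on Days 0 and 28 are untouched. Escalation reviews use data through Day 42 (Sections 4.3 and 11.5), so a scheduled Day 56 ECG lies beyond that cut-off, although an Early Termination ECG could fall within it. The synopsis lists only adverse events and laboratory tests as the primary endpoint; it is Section 4.2 that adds ECGs.

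Most of this stands, and it limits the size of the point. It does not remove it: a probable slip in a visit checklist is still an operative instruction, and nothing in the protocol says which section prevails.

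A reader might go further and infer that ECG change from baseline is not like-for-like at any visit, because the Day 0 ECG is taken after the infusion ("on Days 0 and 28 at 5 minutes after the completion of the infusion"). The protocol does not support that. Section 7.2 lists the Day 0 ECG among the post-treatment procedures, Section 12.5 sets pre-dose as the reference for the shift tables, and screening supplies a supine triplicate pre-dose ECG. Naming the baseline ECG formally is ordinary SAP detail. A baseline up to 14 days old does not prevent the analysis from being carried out as described.

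**Conclusion.** The contradiction is real and limited to the Day 56/Early Termination ECG. Section 7.16 is wrong as written against Section 6.6 and Table 1 note f, and it cites the wrong procedure section.

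The consequence is conditional. Where 7.16 was followed, the three Day 56/ET summaries compare sitting with supine recordings; where sites differ, posture is confounded with site; where 6.6 was followed, nothing is lost. The protocol does not show which practice was used. A reader might infer a definite shift in QTcF, in the same direction for every subject, but the documents give neither a size nor a direction for a posture effect, so none is claimed here. No hypothesis test is affected. The case for correction is that ECGs belong to the safety measure in Section 4.2, that this is the only scheduled recovery ECG, and that correction costs almost nothing.

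**What to change.** - **Text.** In Section 7.16, replace sitting with supine for the ECG and change its cross-reference from Section 6.5 to Section 6.6, so that it agrees with 6.6 and Table 1 note f.
- **Recordings already made.** For Day 56/ET ECGs done before the correction, ask each site which posture was used, and flag sitting recordings in the Section 12.5 change, shift and QTcF summaries.

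The cost is one text edit and one data query per completed Day 56/ET ECG. No visit or procedure is added, and no other ECG time point needs changing.

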#### **7.17 Extended Follow-up Visits**

Extended follow-up visits will occur only if additional testing for anti-tetanus and/ or anti-VZV titers are required. These visits will occur as needed at approximately 2 months post last dose and 3 months post last dose. See [Section 6.7.3](#).

## 8 REMOVING SUBJECTS FROM STUDY

Every reasonable effort will be made to keep the subject in the study; however, if a subject is withdrawn from the study, every effort will be made by the Investigator to complete and report the reasons for withdrawal as thoroughly as possible. The reason(s) for termination must be clearly documented on the appropriate page of the eCRF. Once a subject discontinues from the study for any reason, every effort will be made to collect all clinical and laboratory data as scheduled for the Early Termination Visit (See [Table 1](#)). A termination eCRF must be completed for all enrolled subjects.

### 8.1 Subject Withdrawal

A subject's participation in the study may be prematurely discontinued for any of the following reasons:

1. The subject wishes to withdraw from the study.
2. Request by a regulatory agency (e.g., Institutional Review Board).
3. Subject experiences a significant or intolerable AE.
4. The subject experiences a significant adverse change in vital signs, PE findings, or a clinical laboratory parameter.
5. The subject has a need for a concomitant medication that is not permitted by the study protocol.
6. The subject experiences generalized impairment or mental incompetence that would result in the subject being unable to understand his or her participation in the study.
7. If, in the Investigator's medical judgment, further participation would be injurious to the health and well-being of the subject, or is not in the best interest of the subject.
8. Administrative reasons, such as subject non-compliance or a major protocol violation.

Subjects who are withdrawn from this study due to an AE determined to be related to study drug are to be followed until there is either:

- Resolution or stabilization of the AE determined to be related
- The subject is lost to follow-up
- The event is otherwise explained

If there is a persistent AE contributing to discontinuation that is determined to be related to SYNT001, subjects must be followed with appropriate medical management until resolution or stabilization.

A reasonable effort should be made to contact any subject lost to follow-up during the study to complete assessments and retrieve any outstanding data. If the subjects are unreachable by telephone after three (3) attempts, the minimum of a registered letter should be sent requesting that contact be made with the Investigator to report survival information.

## **8.2 Study Discontinuation**

Syntimmune Inc. has the right to terminate or to stop the study at any time. Reasons for study discontinuation may include, but are not limited to the following:

- The incidence or severity of AEs in this or other related studies indicates a potential health hazard to subjects
- Subject enrollment is unsatisfactory
- Drug supply issues
- Excessive subject self-withdrawal
- Significant protocol violations (e.g., violation of eligibility criteria, dosing errors, missing data for study endpoint analysis)

## **8.3 Replacements**

Enrolled subjects withdrawn for a reason other than an AE will be replaced if they have not been dosed or have only received one dose of study drug at the time of discontinuation, up to one subject per cohort. Subjects who do not receive all doses of study drug will continue to be followed through 28 days after their last dose.

## **8.4 Stopping Rule**

### **8.4.1 Dose-Escalation Stopping Rule**

Dose-limiting toxicity (DLT) will be defined generally as clinically significant, severe (Grade 3) AEs occurring in  $\geq 2$  subjects that are determined to be clinically significant and considered related to study drug.

If 2 or more subjects at any time in any cohort (8 total subjects per cohort) have Grade 3 AEs that are determined to be clinically significant and considered to be related to study drug, dosing will be halted within that cohort and no further dose-escalation will occur. If the dose-escalation

stopping rule is met in Cohort 1 (10 mg/kg) all safety data and all available pharmacodynamics will be reviewed and a cohort may be added at a dose at least 50% lower than the 10 mg/kg dose. If the stopping rule is not met after Cohort 1, dose-escalation may proceed up to a maximum of 30 mg/kg. If the dose-escalation stopping rule is met in Cohort 2, all safety data and all available pharmacodynamics will be reviewed and a cohort may be added at a dose a minimum of 30% lower than the Cohort 2 dose. If the stopping rule is not met after Cohort 2, dose-escalation may proceed up to a maximum of 45 mg/kg; however, this cohort may also receive a dose equal to or less than 30 mg/kg based on evaluation of all safety and pharmacodynamic data.

